and impaired functional recovery. Despite good progress in pain management, ineffective postoperative pain management in children remains a global problem. Regional anesthesia is increasingly used in pediatric patients to provide postoperative analgesia and support intraoperative anesthesia. Ultrasound-guided erector spinae plane block (ESPB) is a new approach. First introduced in 2016 by Forero et al., ESPB is a novel regional anesthesia technique that blocks branches of spinal nerves by injecting a local anesthetic into the fascial plane between the erector spinae muscle and the transverse process. Although new, ESPB has become quite popular due to its ease of application and reliability as a relatively superficial block. Initially, ESPB was defined for chronic pain from the thoracic region. Later, its indications expanded and it is now used in both acute and chronic pain conditions. Applications have also been reported in the lumbar, cervical, and sacral regions, respectively. In recent years, an increasing number of randomized controlled trials (RCTs) have reported that it provides effective postoperative analgesia for thoracic surgeries, nephrectomy, inguinal hernia repair, and laparoscopic cholecystectomy operations in children. In our study, we planned to evaluate the effect of bilateral ESPB on intraoperative anesthetic drug consumption and postoperative pain score and analgesia requirement in pediatric patients operated on due to tethered cord syndrome.

2. Objective

In our study, we aimed to reduce intraoperative anesthetic drug consumption and the level of pain in the first 24 hours postoperatively, the need for analgesics, and unwanted side effects related to analgesics by applying bilateral ESPB in pediatric patients operated on due to tethered cord syndrome.

3. Hypothesis

Bilateral ESPB reduces intraoperative anesthetic drug consumption and the need for postoperative analgesia in pediatric patients operated on due to tethered cord syndrome.

4. Study Phase and Nature

Low-risk scientific study - Prospective randomized controlled single-blind clinical trial

5. Study Population

Pediatric patients undergoing surgery for elective tethered cord syndrome

6. Inclusion Criteria

- Patients whose parents consented to participate in the study
- Patients aged 18 and under
- ASA (American Society of Anesthesiologists) physical status I, II, and III
- Pediatric patients undergoing elective tethered cord syndrome surgery

7. Exclusion Criteria

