- Patients whose parents did not consent to participate in the study

- Patients with ASA physical status IV and V

- Use of anticoagulant medications

- Allergy to local anesthetic drugs

- Patients with a history of gastrointestinal bleeding

- Patients with infection in the area where the block is planned

8. Study Center

Health Sciences University Bursa High Specialization Training and Research Hospital Anesthesiology and Reanimation Clinic

9. Study Duration

1 year

10. Material – Method

Patients included in the study will be divided into 2 groups according to the randomized (closed envelope) sampling method; Erector Spina Plane Block (ESPB, n=34) group and Control group (CG, n=34). Patients who regularly take medication due to cardiovascular or other systemic diseases will continue their medication. Those whose coagulation parameters are checked before the operation and are normal will be included in the study.

The patients' age, height, weight, gender, additional diseases, ASA scores, operation and anesthesia duration, operation level, level of block performed in the group undergoing ESP block, and total anesthetic drug consumption will be recorded. Standard ECG, SpO₂, non-invasive blood pressure (invasive blood pressure monitoring in necessary cases), EtCO₂ and BIS monitoring will be applied in the operating room. After appropriate intravenous access is established in both groups of patients, anesthesia induction will be achieved with 2 mg/kg propofol (Propofol 2%®, FreseniusKabi, Melsungen, Germany), 1 µgr/kg fentanyl (Fentanyl Citrate®, Hospira, USA), and 0.6 mg/kg rocuronium (Esmeron®, Organon, Kloosterstraat, Netherlands). Following intubation, anesthesia maintenance will be administered with a 2 l/min flow rate of 50/50 O₂/air mixture. Inhalation anesthetics will not be used, and no additional doses of muscle relaxants will be given. Neuromonitoring will be performed on all patients by the neurosurgical team following intubation. Patients will be turned to the prone position once they are stable. For total intravenous anesthesia in patients undergoing neuromonitoring-based anesthesia maintenance, propofol will be infused at an initial target plasma concentration of 2.5-4 µg.ml⁻¹ (Medcaptain Shenzhen, Guangdong, CHINA, Elevated model FK/FD). Remifentanil (ULTIVA®, GlaxoSmithKline Parma, Italy) will be infused at a rate of 0.5-1 µg/kg/min. Infusions will be maintained to maintain a BIS of 40-60. Preoperative,

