peroperative 5th, 10th, 15th, 30th, 60th, 90th, 120th, 180th minute, and post-extubation heart rate, supravascular pressure, intravascular pressure, SpO₂, ETCO₂, and BIS values will be recorded.

Patients will be randomly assigned to two separate groups using a sealed envelope method, regardless of their demographic and surgical characteristics. In the ESP Block group, with the patient in the prone position, the research anesthesia team, following aseptic and antiseptic rules, will insert a linear probe (Hitachi Aloka Prosound F31) with a depth of 2-4 cm and a frequency of 10-15 mHz, approximately 2-3 cm lateral to the spinous process, one level above the operative level, in the parasagittal plane, under USG guidance (Hitachi Aloka Prosound F31). After visualizing the transverse process using an in-plane approach, a 50 mm long block needle (Braun Stimuplex® D 0.22 Gax2 in.50mm, Braun, Germany) will be inserted through the skin, passing through the trapezius and erector spinae muscles. When the needle reaches the transverse process (approximately 2-3 cm deep), a test dose of 0.5-1 mL of 0.9% NaCl will be administered between the erector spinae fascia and the vertebral transverse process to confirm the needle's position. After the fascia is seen to be open, a local anesthetic volume of 0.5% bupivacaine (Buvasin, VEM Pharmaceuticals, Turkey) will be calculated as 2 ml per vertebral pressure, not exceeding a maximum dose of 2 mg/kg. This total volume will be diluted half and half with 0.9% NaCl solution to prepare a 0.25% bupivacaine concentration. The calculated local anesthetic solution will be administered to the erector spinae area for ESPB. The same procedures will be performed on the opposite side. No procedure will be performed on the control group. Both groups will receive 15 mg/kg Paracetamol (Parol®, ATABAY, Kurtköy, Pendik, İstanbul) intravenously 20 minutes before the end of surgery. After surgery, patients will be decurarized with 2 mg/kg IV sugammadex (Bridion, MerckSharpDohme, New Jersey, USA), extubated, and taken to the recovery unit. After being admitted to the recovery room, both groups will be assessed using the Wong-Baker FACES™ Pain Rating Scale for children under 5 years old and the FLACC: Pain Rating Scale for children 5 years and older, with pain scores at 0, 5, 10, 15, and 20 minutes. Patients with scores >5 will receive 0.5 mcg/kg fentanyl (TALİNAT®, VEM İlaç, Kapaklı/TEKİRDAG) for rescue analgesia. Paracetamol 15 mg/kg/6 hours will be administered intravenously for postoperative analgesia. A blinded investigator will assess patients' pain scores, analgesic requirements, names of analgesics administered, and nausea/vomiting at 30 minutes, 1, 2, 4, 6, 12, and 24 hours postoperatively. The time and dose of the first postoperative analgesic, and length of hospital stay will be recorded.

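### The only person the protocol describes as blinded is the 30-minute to 24-hour outcome investigator; nothing withholds the arm from the child, family, recovery-room or ward staff, although concealment is feasible

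*Combined protocol and SAP*

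**What the plan says.** Section 4 describes the design as "Low-risk scientific study - Prospective randomized controlled single-blind clinical trial". It does not say who the blinded party is.

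Section 10 contains the only mention of a blinded person: "A blinded investigator will assess patients' pain scores, analgesic requirements, names of analgesics administered, and nausea/vomiting", at seven times from 30 minutes to 24 hours after surgery. The earlier recovery-room scoring, "with pain scores at 0, 5, 10, 15, and 20 minutes", is not assigned to anyone, and whoever does it is not said to be blinded.

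On what could reveal the arm, section 10 says of the controls "No procedure will be performed on the control group". No sham or dummy dressing is described, and no rule covers what goes into the chart or the hand-over. The block level is recorded, but where that record is kept is not stated.

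On timing, section 10 says "After appropriate intravenous access is established in both groups of patients, anesthesia induction will be achieved with 2 mg/kg propofol", then, after intubation, "Patients will be turned to the prone position once they are stable". The block itself follows: "In the ESP Block group, with the patient in the prone position, the research anesthesia team" carries it out.

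Section 3 gives the hypothesis: "Bilateral ESPB reduces intraoperative anesthetic drug consumption and the need for postoperative analgesia".

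**The concern.** The blinded investigator observes and records; other people produce part of what is recorded. A self-reported pain score comes from the child. The need for an analgesic, its name, and the time and dose of the first one depend on whoever asks for, decides on and gives the drug. If those people know the arm, a blinded recorder copies down a quantity that their knowledge may already have shaped, and none of the analyses in section 13 can separate that influence from a true block effect.

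Analgesic need is one of the two limbs of the hypothesis, so a main conclusion of the trial is exposed. The sealed envelopes do not help: they hide the allocation before assignment and blind nobody afterwards.

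**Working it through.** **Step 1. Who produces each postoperative outcome, as section 10 is written**

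- *Recovery-room scores, 0 to 20 minutes:* scorer not named; blinding not stated.
- *Fentanyl rescue:* triggered by a score above 5, in the sentence that follows the recovery-room scoring. It inherits any bias in the score. No separate trigger is given for later hours.
- *Scores from 30 minutes to 24 hours, age 5 and over:* FLACC, which is observer-rated. The blinded investigator protects these in part.
- *Scores from 30 minutes to 24 hours, under 5:* Wong-Baker FACES, which is self-report. The score comes from the child, whose blinding is not stated.
- *Paracetamol:* fixed schedule in both arms. Knowledge of the arm has no stated route to it.
- *Any other analgesic:* need and name are recorded, but no rule for giving it is stated. Knowledge of the arm can act here.
- *Time and dose of the first analgesic:* inherits whatever applies to the drug concerned.

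The exposure is therefore real but limited to the recovery-room scores and the rescue that follows from them, the self-reported scores, and analgesics outside the two stated rules.

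**Step 2. Is concealment feasible?** The order in section 10 is induction, intubation, turning prone, then block. The child cannot observe it. Family, recovery-room and ward staff would learn the arm only by being told, from the chart, or from the skin. The skin matters: the block leaves punctures on both sides, 2 to 3 cm from the spinous process and one level above the operation, and controls have none.

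**Step 3. Reproduce the plan's sample size.** Inputs from section 13: effect size 0.70, power 80%, 95% confidence level, 34 + 34 patients. A two-sample t-test (the same as ANOVA with two groups), two-sided alpha 0.05, 1:1, gives 33.02, rounded up to 34 per arm, 68 in total. Power at 34 per arm is 0.812. A one-sided test would give 26 per arm, so the stated figure is two-sided.

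**Step 4. Illustrate the stakes with the same test.** Assume no true block effect and a spurious mean shift of b SD between arms. The test statistic is noncentral t with 34 + 34 − 2 = 66 degrees of freedom and noncentrality b × √(34/2) = b × 4.123. The false-positive rate is the probability that its absolute value exceeds the two-sided 5% critical value.

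| Assumed shift b (SD) | Noncentrality | Share of planned 0.70 | Chance of p<0.05 |
|---|---|---|---|
| 0 | 0 | 0% | 5.0% |
| 0.1 | 0.41 | 14% | 6.9% |
| 0.2 | 0.82 | 29% | 12.8% |
| 0.3 | 1.24 | 43% | 23.0% |
| 0.4 | 1.65 | 57% | 36.9% |

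The shifts are assumptions; nothing in the documents supports one row over another.

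**The case against.** The strongest reply is that all this argues from silence. The single-blind label names no party, what families are told may be set out in consent material that is not part of the public text, and an assessor-blinded design is a legitimate meaning of the label. The routes for bias are also narrow: paracetamol is fixed, rescue has a threshold, no outcome is rated or triggered by parents, and self-report is used, as written, only in children under 5, in whom an expectation effect is least plausible.

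Much of this stands, and it rules out four stronger readings that a reader might infer:

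- *That the blind covers only the investigator.* The text supports only that the investigator is the one person described as blinded.
- *That families or staff will know the arm and act on it.* Nobody outside the theatre team is documented as knowing it, and the parents' part is ordinary paediatric care rather than anything in the protocol.
- *That the bias must favour the block.* This is plausible, but neither direction nor size is documented.
- *That sections 4 and 10 contradict each other.* They would conflict only if single-blind meant participant-blind; read as assessor-blind, they agree.

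The reply does not close the gap. Recovery-room and ward practice is a matter for the protocol, which has no instruction to withhold the arm there. It records the names of analgesics and the need for them without a rule governing drugs beyond paracetamol and the rescue dose, so room for discretion remains. A threshold does not protect rescue when the scorer may know the arm.

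**Conclusion.** The point holds in this limited form. A trial run exactly as written could let those who generate part of the analgesic-need data know the allocation, and the plan gives no means of preventing or detecting it. It should be corrected, because concealment is practicable and inexpensive and the bias could not be removed in analysis.

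The size is unknown. The range of about 7% to 37% rests on assumed shifts of 0.1 to 0.4 SD applied in full to the arm comparison. With part of the data protected by fixed dosing and a blinded FLACC rater, the effective shift could be at the low end, where the inflation is small. Confidence is medium: the absence of any withholding rule is plain from the text, but the strength of the pathway is inferred.

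**What to change.** In sections 4 and 10:

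1. State that the child, the parents, the recovery-room staff and the ward staff are not told the allocation until the 24-hour assessment is complete.
2. Keep the opened envelope and the block record in a separate research file with emergency access.
3. Use the same hand-over wording for every child, saying that the child is in the study and may have received local anaesthetic.
4. Apply identical dressings over the potential puncture sites in both arms. Without this, calling the family or ward staff blinded would not be credible.
5. Replace the single-blind label with a list of the parties actually blinded, and say that the theatre anaesthesia team is not.

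The cost is protocol and consent wording, a separate file, and dressings for all 68 children. No additional patients are needed and the sample size does not change. The one drawback is that staff must open the emergency file if they need to know whether bupivacaine was given. These steps do not blind the theatre team, so they leave the intraoperative drug-consumption limb of the hypothesis as it is.

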
11. Research Budget

The cost of 34 block needles and 34 doses of the drug buvasin containing the active ingredient bupivacaine for one patient has been submitted with a propharmaceutical invoice. The expenses will be covered by the researchers.

12. Ethics Committee Approval

An application has been submitted for ethics committee approval.

13. Statistics

Statistical analyses of the obtained data will be performed using the IBM SPSS Statistics 21.0 software package. Descriptive statistics of the data will include mean, standard deviation, frequency, and percentage values. Chi-square and FischerExact tests will be used for the analysis of categorical variables. The normality assumption of continuous numerical variables will be checked separately in groups using the Shapiro-Wilk test. Analysis of variance (ANOVA) will be used for independent group

comparisons of numerical variables showing normal distribution. Kruskal-Wallis (KW) test will be used for variables that do not show normal distribution. For comparisons of consecutive measurements, the Wilcoxon Signed Ranks test will be used for pairs of measurements, the Friedman test for more than two measurements, and the Pearson correlation test will be used as a correlation test. The significance level will be set at $p<0.05$ in all analyses. The required sample size for the study was calculated as 68 (34+34) patients in total, including the group that underwent ESPB and the group that did not undergo ESPB, with an effect size of 0.70, 80% test power, and 95% confidence level. The relevant calculations were made in the G-Power 3.1.9.2 software package.

14. References

1. Gado, A. A., Alsadek, W. M., Ali, H., & Ismail, A. A. (2022). Erector spinae plane block for children undergoing cardiac surgeries via sternotomy: a randomized controlled trial Anesth Pain Med. 2022;12(2):e123723. doi: 10.5812/aampm-123723. PMID: 35991776
2. Aksu, C., & Gürkan, Y. (2018). Ultrasound guided erector spinae block for postoperative analgesia in pediatric nephrectomy surgeries. J Clin Anesth. 2018 Mar;45:35-36 doi: 10.1016/j.jclinane.2017.12.021. Epub 2017 Dec 20. PMID: 29274546

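### Time to first analgesic is not separated from scheduled paracetamol, and section 13 has no rule for children who never need rescue

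*Combined protocol and SAP*

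**What the plan says.** **Outcome.** Section 10 (Material – Method) ends its data list with "The time and dose of the first postoperative analgesic, and length of hospital stay will be recorded". It names no drug class and ties no starting point to this time.

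**Analgesics.** The same section describes two kinds of analgesic after surgery:
- A scheduled one for every child: "Paracetamol 15 mg/kg/6 hours will be administered intravenously for postoperative analgesia". No time is given for the first postoperative dose. Both arms also receive a paracetamol dose "intravenously 20 minutes before the end of surgery".
- A conditional one: "Patients with scores >5 will receive 0.5 mcg/kg fentanyl", described as rescue. The sentence follows the recovery-room scores taken at 0 to 20 minutes.

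**Other data.** A blinded investigator also records "analgesic requirements, names of analgesics administered, and nausea/vomiting at 30 minutes, 1, 2, 4, 6, 12, and 24 hours postoperatively".

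**Role of the outcome.** Section 2 aims to reduce "the level of pain in the first 24 hours postoperatively, the need for analgesics". Section 3 states: "Bilateral ESPB reduces intraoperative anesthetic drug consumption and the need for postoperative analgesia in pediatric patients". No primary outcome is named.

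**Analysis.** Section 13 gives ANOVA for normally distributed numerical variables, and "Kruskal-Wallis (KW) test will be used for variables that do not show normal distribution". Chi-square and Fisher tests are listed for categorical variables. There is no time-to-event method, no censoring rule and no value for a child without a rescue.

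**The concern.** The variable can be read in two ways, and each causes trouble under the listed tests.

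1. **Paracetamol counts.** The wording of the outcome is closer to the paracetamol sentence than to the rescue sentence, so this is a literal reading. No child's time can then exceed the first scheduled dose, and much of the variable records the schedule rather than need.
2. **Only rescue counts.** Many readers would assume this. Rescue depends on a score, so some children will have no time at all, and there will be more of them under ESPB if the hypothesis is true. A test on the recorded times then compares rescued children only. That selection happens after randomisation and may be affected by treatment.

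At stake is one of several measures of the need for analgesia named in the hypothesis. The same 68 children could show a small, a moderate or an exaggerated gain in hours, depending on a reading chosen after the data are seen.

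**Working it through.** **The plan's own figure.** Section 13 gives effect size 0.70, 80% power and 95% confidence. A two-sided two-sample t-test needs 33.02 per arm, rounded up to 34, so 68 in total (power at 34 per arm 0.812). The stated size is reproduced. The 0.70 is not tied to any outcome, so the present point does not alter it.

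**Assumptions.** The documents give no rescue rates, no rescue timing and no time for the first postoperative paracetamol. Everything below is illustrative: 34 per arm (section 10), a 24 h horizon (the last assessment), and two-sided 0.05. If 6 h is counted from the dose given 20 minutes before the end of surgery, the first scheduled dose falls at 6 h − 20 min = 5 h 40 min (5.667 h).

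**Case 1: constant hazard, 70% v 35% rescued by 24 h.** The hazard is λ = −ln(1 − p)/24.
- Control: 1.2040/24 = 0.05017 per hour. ESPB: 0.4308/24 = 0.01795 per hour.
- Expected never rescued: 0.30 × 34 ≈ 10 control and 0.65 × 34 ≈ 22 ESPB, so about 32 of 68.
- Mean time cut at c hours: (1 − e^(−λc))/λ.
- *24 h assigned (c = 24):* 0.35/0.01795 − 0.70/0.05017 = 19.50 − 13.95 = **5.5 h**.
- *Dropped:* the mean among the rescued is (mean cut at 24 h − 24(1 − p))/p. ESPB (19.50 − 15.60)/0.35 = 11.14; control (13.95 − 7.20)/0.70 = 9.65; difference **1.5 h**.
- *Counted (c = 5.667):* 5.388 − 4.932 = **0.46 h**. With c = 1 h it would be 0.991 − 0.975 = 0.02 h, so this figure depends heavily on the unstated dosing time.

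Simulated power at 34 per arm:

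| Handling | Power, Case 1 |
|---|---|
| Kruskal-Wallis, 24 h assigned | 0.83–0.84 |
| Kruskal-Wallis, never-rescued dropped | 0.08–0.10 |
| Kruskal-Wallis, paracetamol counted, all at 5 h 40 min | 0.37 |
| Kruskal-Wallis, paracetamol counted, first dose spread over 5–6 h | 0.17 |
| Log-rank, censored at 24 h | 0.86 |
| Fisher on proportion rescued | 0.75–0.77 |

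**Case 2: delay only, 60% rescued in both arms.** Control times are uniform over 0–6 h (mean 3), ESPB over 4–14 h (mean 9).
- *24 h assigned:* 0.6 × (9 − 3) = **3.6 h**.
- *Dropped:* 9 − 3 = **6.0 h**, an overstatement.
- *Counted at 5.667 h:* the capped means among the rescued are 5.667 − 5.667²/12 = 2.991 (control) and 5.667 − 1.667²/20 = 5.528 (ESPB). The difference is 0.6 × 2.537 = **1.5 h**.
- Kruskal-Wallis power is 0.70 with 24 h assigned and 0.95–1.00 with paracetamol counted. Here counting shrinks the hours but raises rank-test power.

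**Case 3: rescue confined to the first 20 minutes, 70% v 35%, same timing in both arms.** Dropping leaves a difference of 0.0 h and power of 0.05. Counting paracetamol gives 0.72–0.77, against 0.77 for Kruskal-Wallis with 24 h assigned, so it costs little.

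**Where the shrinkage fails.** Suppose control children are rescued 60% at 2 h and ESPB children 90% at 10 h.
- *24 h assigned:* (0.9 × 10 + 0.1 × 24) − (0.6 × 2 + 0.4 × 24) = 11.4 − 10.8 = 0.6 h.
- *Counted at 5.667 h:* 5.667 − (0.6 × 2 + 0.4 × 5.667) = 2.2 h, which is wider.

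So the direction needs the condition that ESPB does not raise the share eventually rescued.

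**The case against.** Several objections have force.

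- **A natural reading exists.** Fentanyl is labelled rescue and paracetamol is a fixed schedule, so rescue only is a fair guess. This stands, but that reading still lacks a value for the never-rescued child.
- **Dropping is not planned.** A reader might infer that the sponsor intends to exclude never-rescued children. The documents do not say so. Exclusion is simply what the listed tests do with missing times when nothing is assigned.
- **Counting paracetamol does not always harm.** A reader might infer that it always shrinks the difference or always costs power. Neither holds: the crossing example widens the hours, and Case 2 gains power. The 24 h and 5 h 40 min figures also cover different horizons, so part of the shrinkage is simply the shorter window.
- **Other data protect the question.** Drug names are recorded to 24 h, so fentanyl can be separated from paracetamol and the proportion rescued compared with a test already listed. This stands and limits the harm, although the plan does not commit to that comparison.
- **The starting point has no shown effect.** No time zero is stated, but nothing suggests that the choice would differ by arm. It needs fixing only for definiteness.
- **Kruskal-Wallis is not always strong.** With a milder delay (60% in both arms, 0–6 h v 1–8 h), its power with 24 h assigned is 0.18, against 0.10 for log-rank. The case for it is that it is already listed and keeps every child in the analysis.

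**Conclusion.** The point holds in limited form. As written, the measure either includes a scheduled drug or has no value for some children, and section 13 settles neither. With 70% v 35% rescued at constant hazard, the same data would give about 5.5 h, 1.5 h or 0.46 h. With delay only, dropping turns 3.6 h into 6.0 h. These sizes rest on assumed rates, and the counted figures also rest on an assumed first paracetamol time. The objection to analysing rescued children only does not depend on the rates, because the selection occurs after randomisation.

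A reader might go further and infer that the trial cannot answer its question about analgesic need, or that 68 children is the wrong number. The documents do not support either: this is one recorded measure among several, the proportion rescued remains available, and the sample size is not built on it. It should be corrected before data are seen, but it does not threaten the trial as a whole.

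**What to change.** **Section 10.** Define the outcome as time from recovery-room arrival, the same origin in both arms, to the first unscheduled rescue analgesic within 24 h. State that scheduled paracetamol does not count. Recovery-room arrival is one reasonable origin; what matters is that one is fixed.

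**Section 13.** Include all randomised children. Assign 24 h to those never rescued, so that they rank longest, and compare the arms by Kruskal-Wallis whatever the normality test shows. Report the proportion rescued by chi-square or Fisher. Kaplan-Meier curves may be added as description.

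**Cost.** One sentence in each section, one field on the data form for the time of first rescue, and slightly more analysis. Treatment and sample size are unchanged, and both tests are already listed.

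**Separately**, the sponsor should state whether the sentence on scores above 5 covers the recovery room only or the full 24 h, since this decides when a rescue can occur. No clinical rule is proposed here.

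### The arm comparison of intraoperative heart rate and blood pressure makes no use of each child's own preoperative value, so it is less precise than the collected data allow and can miss a haemodynamic difference.

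*Combined protocol and SAP*

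**What the plan says.** The recording schedule in Section 10 (Material – Method) starts with a preoperative reading, named straight after the sentence on titration: "Infusions will be maintained to maintain a BIS of 40-60. Preoperative". It continues with "peroperative 5th, 10th, 15th, 30th, 60th, 90th, 120th, 180th minute, and post-extubation heart rate, supravascular pressure, intravascular pressure", followed by SpO₂, EtCO₂ and BIS. The two pressure terms look like translation slips for systolic and diastolic, and are read that way here. Each child therefore has one preoperative value, eight intraoperative values and one post-extubation value of each variable.

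Section 6 admits "Patients aged 18 and under" and sets no lower limit. Section 10 allocates children "regardless of their demographic and surgical characteristics", so age is not balanced by design.

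For numerical variables Section 13 (Statistics) states: "Analysis of variance (ANOVA) will be used for independent group" comparisons under normality; otherwise, "Kruskal-Wallis (KW) test will be used for variables that do not show normal distribution". For repeated readings it says: "For comparisons of consecutive measurements, the Wilcoxon Signed Ranks test will be used for pairs of measurements", with Friedman for more than two. No analysis of covariance, mixed model, change from baseline, arm-by-time term or age adjustment appears anywhere.

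**The concern.** Normal heart rate and blood pressure change a great deal between infancy and late adolescence. If ages are mixed within each arm, much of the spread in a raw intraoperative value reflects who the child is, not what happened in theatre. A one-way ANOVA or Kruskal-Wallis test leaves all of that spread in the error term. The preoperative reading of the same variable could remove part of it and is already being collected.

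The Wilcoxon and Friedman tests do not fill the gap. They use a child's own values but test change over time within patients. A significant change in one arm and not in the other is not a comparison of the arms.

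At stake are the main recorded data that could show a haemodynamic difference between block and control, whether wanted or unwanted. A low-powered finding of no difference could be read as reassurance.

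**Working it through.** **Inputs from the documents.** 34 per arm, effect size 0.70, 80% power, significance level 0.05 (Section 13). Sidedness is not stated. No outcome is attached to the 0.70.

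**Inputs assumed.** The correlation ρ between the preoperative and a later value is not given, so it is shown over a range. Effects are in units of the SD of the raw later value, because no SD is given. The preoperative and later SDs are taken as equal where that matters.

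**1. Reproduce the plan's sample size.** With two arms, one-way ANOVA is equivalent to the two-sample t-test. Power comes from the noncentral t distribution with noncentrality d·√(n/2) on 2n − 2 degrees of freedom. For d = 0.70 and n = 34: 0.70 × √17 = 2.886 on 66 degrees of freedom, two-sided 0.05, power 81.2%. At n = 33 power is 79.97%, just short of 80%. So 34 per arm, 68 in total, reproduces as a two-sided unadjusted test. A one-sided test would need about 26 per arm and does not match.

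**2. Effect of using the baseline.** With the preoperative value as covariate, the residual SD is SD × √(1 − ρ²), so the standardised effect becomes d/√(1 − ρ²), on 65 degrees of freedom. For a true difference of 0.5 SD with 34 per arm:

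| Analysis | Residual SD | Noncentrality | Power | Difference detectable at 80% power |
|---|---|---|---|---|
| Unadjusted | 1.000 | 0.500 × √17 = 2.06 | 53% | 0.69 SD |
| Adjusted, ρ = 0.3 | 0.954 | 0.524 × √17 = 2.16 | 57% | 0.66 SD |
| Adjusted, ρ = 0.5 | 0.866 | 0.577 × √17 = 2.38 | 65% | 0.60 SD |
| Adjusted, ρ = 0.7 | 0.714 | 0.700 × √17 = 2.89 | 81% | 0.49 SD |

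**3. Why not a simple change score.** Its SD is SD × √(2(1 − ρ)): 1.183 at ρ = 0.3, 1.000 at 0.5 and 0.775 at 0.7. Power for the same 0.5 SD difference is 40%, 53% and 75%. It is worse than the raw value below ρ = 0.5, only breaks even at 0.5, and is below covariance adjustment at all three values.

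**4. Chance baseline imbalance.** The SD of the difference in preoperative means is √(2/34) = 0.243 SD. The chance that it exceeds 0.3 SD in either direction is 2 × [1 − Φ(0.3/0.243)] = 21.6%. The expected carry-over to the later comparison is ρ times the imbalance: at ρ = 0.5, 0.5 × 0.3 = 0.15 SD.

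**The case against.** The strongest reply is that these are not outcomes the trial sets out to test. The objective and hypothesis (Sections 2 and 3) concern anaesthetic consumption, postoperative pain, analgesic need and side effects. Heart rate and pressure are simply recorded, and the haemodynamic arm comparison is inferred from a general sentence about numerical variables. This stands, and it limits the point to secondary or safety data.

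A reader might infer several stronger things that the documents do not support:

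- **That the raw analysis is biased, or does hide a block effect.** It is neither shown nor implied. Randomisation keeps the unadjusted comparison unbiased, and its standard error already allows for chance imbalance. Only about ρ times an imbalance carries over, not all of it. The age spread can hide a difference; whether it will depends on the ages enrolled, which are unknown.
- **That the plan's 0.70 applies to heart rate or pressure.** Section 13 ties it to no outcome, so power gains computed at 0.70 are not the plan's own figures for these variables. The 0.5 SD above is equally an illustration.
- **That adjustment would isolate a block-related fall.** The preoperative reading precedes induction, intubation and prone positioning. No reading immediately before the block is specified, and time zero for the minute readings is not defined. Adjustment sharpens the contrast between arms; within a child it cannot separate a fall due to the block from one due to induction.
- **That the same argument covers SpO₂.** It does not: the age argument concerns heart rate and pressure.

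It is also fair to say that preoperative readings in anxious children may track later values poorly, in which case ρ and the gain are small.

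**Conclusion.** The point holds as a low-stakes gain in efficiency. No planned arm comparison uses the preoperative value of the same variable, although it is collected in every child and the eligible age range makes large stable differences between children likely. The cost is lost precision, not bias. For a 0.5 SD difference with 34 per arm, adjustment would raise power from 53% to 57% at ρ = 0.3, 65% at 0.5 and 81% at 0.7. These figures rest on an assumed effect and assumed correlations, and at the low end the gain is slight. The stated sample size reproduces and is not called into question.

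**What to change.** In Section 13, add that arms will be compared on heart rate and the two pressures with the child's own preoperative value of the same variable as covariate. This can be an analysis of covariance at each time, or one repeated-measures model per variable with arm, time and arm-by-time. The second avoids 3 × 9 = 27 separate tests. Report adjusted arm differences with 95% confidence intervals. If residuals are clearly non-normal, fit the same model to ranks. Do not use simple change scores.

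Leave SpO₂ out of this change. Do not add a summary of the lowest value as a percentage of baseline: it would mix induction with block effects and depend on how many readings a child has, since the late ones will be missing after shorter operations.

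State in the text that the baseline precedes induction, so the model compares arms and does not attribute a fall within a child to the block.

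The cost is a sentence or two of wording and one residual degree of freedom in each covariance analysis (66 to 65). No new data, visits or patients are needed, and the model can be run in the SPSS package already named. If the correlation proves low, little is gained, but little is lost.
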